### **6.3.4 ECG**

#### **Resting 12-lead ECG**

A 12-lead ECG will be performed at the time points according to the study schedule ([Table 5](#), [Table 8](#), [Table 9](#) and [Table 12](#)). All ECGs should be performed prior to PK sampling for corresponding time points.

The timing and number of ECGs may be altered depending on the emerging PK and safety profile.

Twelve-lead ECGs will be obtained after the subject has been resting semi-supine for at least 10 minutes prior to times indicated. All ECGs should be recorded with the subject in the same physical position. For each time point three ECG recordings should be taken at not more than 5-minute intervals. A standardised ECG machine should be used and the subject should be examined using the same machine throughout the study if possible.

After paper ECGs have been recorded, the investigator or sub-investigators will review each of the ECGs and may refer to a local cardiologist if appropriate. A paper copy should be filed in the subject’s medical records.

If an abnormal ECG finding at screening or baseline is considered to be clinically significant by the investigator, it should be reported as a concurrent condition, and the eligibility of the subject should be evaluated. The investigator or sub-investigator should assess the ECG records for abnormality and record the result.

### **6.3.5 Laboratory safety assessment**

Blood and urine samples for determination of haematology, clinical chemistry, and urinalysis will be taken at the visits as indicated in the study schedule (see [Table 5](#) and [Table 9](#)). All assessment timepoints are based on Day 1 as first dose of MEDI-573 and are to be taken with this baseline. Laboratory tests are done on treatment day, it should be done prior to infusion. Laboratory tests do not need to be repeated at baseline if the baseline visit is within 3 days of the screening sample.

The date of each collection will be recorded in the appropriate CRF.

Date

Following review of data from a group of subjects the timing of blood samples may be adjusted for subsequent groups of subject. Laboratory values that meet the criteria for CTCAE grade 3 or have changed significantly from baseline and are considered to be of clinical concern will be repeated/confirmed within 7 days and followed up as appropriate.

The following laboratory variables will be measured:

### **Clinical chemistry**

Albumin	Bilirubin, total
ALT	Calcium, total
AST	Creatinine
Alkaline phosphatase	LDH
Magnesium	Chloride
Phosphorus	Glucose
Potassium	BUN
Sodium	TSH ( at Day 1 of every cycle and end of treatment only )
	HbA1c (at Screening and end of treatment only )

### **Haematology**

Haemoglobin	Absolute leukocyte differential count:
Leukocyte Esterase	Neutrophils
Platelet count	Lymphocytes
	Monocytes
	Basophils
	Eosinophils

### **Urinalysis**

PH	Glucose
Protein	Ketones
Bilirubin	Blood

Additionally a serum sample will be collected from all female subjects of child-bearing potential at screening, a urine sample will be collected on Day 1 of every cycle and 30 days after the last dose of MEDI-573 for a pregnancy test.

For blood volume see Section [6.8.1](#).

Date

### **6.3.6 Follow-up**

A post study assessment will be performed at the time investigational product is permanently discontinued (see [Table 5](#) and [Table 9](#)).

In addition subjects should be followed up at 30 days after the last dose of study treatment for any new reports of AEs. Subjects should also be asked about concomitant medications at this follow-up. IM and preliminary anti-tumour activity will be evaluated at the follow-up, which occurs 3 months after the last dose (see [Table 5](#) and [Table 9](#)).

## **6.4 Adverse events**

The Principal Investigator is responsible for ensuring that all staff involved in the study is familiar with the content of this section.

### **6.4.1 Definition of adverse events**

An AE is the development of an undesirable medical condition or the deterioration of a pre-existing medical condition following or during exposure to a pharmaceutical product, whether or not considered causally related to the product. An undesirable medical condition can be symptoms (eg, nausea, chest pain), signs (eg, tachycardia, enlarged liver) or the abnormal results of an investigation (eg, laboratory findings, electrocardiogram). In this clinical study, an AE can include an undesirable medical condition occurring at any time from the time of informed consent until 30 days after the last infusion of MEDI-573, even if no study treatment has been administered.

For cases where it could be suspected that a tissue-derived medicine has been contaminated by a pathogen, information about any of the above conditions (including infection) should be collected.

Any deterioration of the disease under study and associated symptoms or findings should not be regarded as an AE as far as the deterioration can be anticipated.

The term AE is used generally to include any AE whether serious or non-serious.

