### **Adverse events based on examinations and tests**

The results from protocol mandated laboratory tests, vital signs, ECGs and other safety assessments will be summarised in the Clinical Study Report. Deterioration as compared to baseline in these parameters will therefore only be reported as AEs if they fulfil any of the criteria for a SAE or DLT, or are the reason for discontinuation of treatment with the investigational product unless clearly due to progression of disease under study (see Disease progression).

If deterioration in a laboratory value, vital sign, ECG or other safety assessment is associated with clinical signs and symptoms, the sign or symptom will be reported as an AE and the associated laboratory result or other finding will be considered as additional information.

Date

Wherever possible the reporting investigator uses the clinical, rather than the laboratory term (eg, anaemia versus low haemoglobin value).

Deterioration of a laboratory value that is unequivocally due to disease progression should not be reported as an AE.

Any new or aggravated clinically relevant abnormal medical finding at a physical examination as compared with the baseline assessment will be reported as an AE.

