### **Disease progression**

Disease progression can be considered as a worsening of a subject's condition attributable to the disease for which the investigational product is being studied. It may be an increase in the severity of the disease under study and/or increases in the symptoms of the disease. The development of new, or progression of existing metastasis to the primary cancer under study should be considered as disease progression and not an AE. Events that are unequivocally due to disease progression should not be reported as AEs during the study.

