### **Handling of deaths**

All deaths that occur during the study, or until 30 days after the last dose of MEDI-573, should be reported as follows:

- Death, which is unequivocally due to disease progression, should be communicated to the study monitor at the next monitoring visit and should be documented in the CRF module, but should not be reported as a SAE during the study
- Where death is not clearly due to disease progression of the disease under study the AE causing the death should be reported to the study monitor as an SAE within 1 day. The report should contain a comment regarding the co-involvement of progression of disease, if appropriate, and should assign a single primary cause of death together with any contributory causes
- Deaths with an unknown cause should always be reported as a SAE but every effort should be made to establish a cause of death. A post-mortem may be helpful in the assessment of the cause of death, and if performed a copy of the post-mortem results (with translation of important parts into English) should be reported in an expedited fashion to an AstraZeneca representative within the usual timeframes.

Date

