## **7. EVALUATION AND CALCULATION OF VARIABLES AND STATISTICAL METHODS**

### **7.1 Definition of study endpoints**

To meet the objectives for this study, data for the following endpoints will be collected:

- Safety and Tolerability (Primary)
- MTD and/or optimal biologic dose, if possible (Secondary)
- MEDI-573 PK (Secondary)
- IM (Secondary)
- Pharmacodynamics (Secondary)
- MEDI-573 Tumour response (Secondary)
- Exploratory biomarkers (levels of circulating soluble protein biomarkers including GH, IGF1, insulin and glucose, and levels of phosphorylated and/or factors biomarkers in specimens including IGF-1R, IRS-1, MAPK, ERK, Ki67, caspase 3, and/or AKT) (Exploratory)
- Pharmacogenetics (Exploratory)

Safety endpoints are defined in Sections 6.3 and 6.4. Calculations and analysis plans for each of these endpoints are presented below.

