### **7.3 Calculation or derivation of safety variables**

Safety and tolerability will be assessed in terms of AEs, laboratory data, vital signs and ECG changes. These will be collected for all subjects.

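### Sections 6.4.1 and 6.4.3 use different tests (foreseeable versus unequivocally due to progression) to keep disease-related events out of the AE record, and neither is given precedence.

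*Protocol*

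**What the plan says.** Protocol section 6.4.1 defines an AE broadly, without regard to causality, and then makes an exception. Deterioration of the disease under study, with the symptoms or findings that go with it, "should not be regarded as an AE as far as the deterioration can be anticipated".

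Section 6.4.3 returns to the subject under several sub-headings:

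- Disease progression: "Events that are unequivocally due to disease progression should not be reported as AEs during the study". New or progressing metastasis "should be considered as disease progression and not an AE", with no condition attached.
- Adverse events based on examinations and tests: "Deterioration of a laboratory value that is unequivocally due to disease progression should not be reported as an AE". The same sub-section reports certain test deteriorations as AEs "unless clearly due to progression of disease under study".
- Handling of deaths: "Death, which is unequivocally due to disease progression" is documented in the CRF but not reported as an SAE. The next bullet, on deaths that are to be reported, asks instead whether the death is clearly due to progression.

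Section 7.1 makes safety and tolerability the primary endpoint, and section 7.3 states: "Safety and tolerability will be assessed in terms of AEs, laboratory data, vital signs and ECG changes". Under section 3.1 the study is single-arm, at one site, with 3 to 6 evaluable subjects per cohort and 9 to 18 in total.

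**The concern.** The two sections set different conditions for leaving a disease-related event out of the AE record. Whether worsening was foreseeable is a judgement about the expected course of the illness. Whether it is unequivocally due to progression is a judgement about how sure one is of the cause. In patients with refractory advanced tumours, worsening is often foreseeable while the cause of a particular symptom remains uncertain.

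The classification carries through the safety record. Section 6.4.2 defines an SAE as an AE that meets a seriousness criterion, and section 6.4.3 collects the CTCAE grade and the causality answer for each AE. A symptom left out by definition is not graded or rated for causality on the AE form and cannot be reported as an SAE. With no control group, there is no second arm in which the same practice would show.

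**Working it through.** The protocol states no figure on this point, so the check is a comparison of the two rules.

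**Inputs.** Rule A is the 6.4.1 exception: disease deterioration and its symptoms are not AEs if they could be anticipated. Rule B is the 6.4.3 Disease progression paragraph: events are not reported if unequivocally due to progression. Take events that the investigator attributes to the disease and classify them by both tests. Metastatic progression is set aside, because 6.4.3 excludes it without condition.

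1. Anticipated and unequivocally due to progression: out under A, out under B. The rules agree.
2. Anticipated but not unequivocally due to progression: out under A, reportable under B. The rules conflict. An example is a symptom regarded as tumour-related in which a drug contribution cannot be ruled out.
3. Not anticipated but unequivocally due to progression: an AE under A, not reported under B. The rules conflict the other way.
4. Neither: an AE under both. The rules agree.

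The rules disagree in two of the four cells, in opposite directions. Neither test contains the other, so applying the stricter one does not satisfy both.

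**Wording within 6.4.3.** Events, laboratory values and the first bullet on deaths use the unequivocal standard. The general rule on tests and the second bullet on deaths use the word clearly. A death that is clearly but not unequivocally due to progression falls under neither bullet as written.

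**Weight of one subject.** If one subject moves from having an event to not having it, the incidence changes by 1/n:

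- cohort of 6: 1/6 = 16.7 percentage points
- cohort of 3: 1/3 = 33.3 percentage points
- 18 subjects in total: 1/18 = 5.6 percentage points
- 9 subjects in total: 1/9 = 11.1 percentage points

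These use the evaluable numbers. The safety set in Table 20 contains everyone who received a dose, so it may be somewhat larger and the shifts somewhat smaller. The figures are the weight of any single subject in cohorts of this size. They do not estimate how often cells 2 and 3 would occur, and the protocol gives nothing from which to estimate that.

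**The case against.** The strongest defence is that 6.4.1 reaches only deterioration of the disease under study. An event must first be judged to be disease worsening, and only then does foreseeability matter. Fatigue that might be drug or disease has not passed that first step, and the AE definition does not require a causal link to the drug. Section 6.4.3 can then be read as the specific recording rule that a site would follow when completing the CRF.

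The first part stands as a limit. A reader might infer that 6.4.1 removes nearly every symptom expected in advanced cancer. The text does not say that. But 6.4.1 sets no degree of certainty for the judgement that a symptom belongs to the disease, whereas 6.4.3 does, and cell 3 conflicts even if attribution is settled. The second part is a sensible reading that the protocol does not state. Recording rules apply to AEs, so an event that the definition has already excluded need never reach the stricter test. Having one site removes differences between sites but does not tell its investigators which rule to use.

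Other stronger inferences also fail:

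- **AE incidence as the whole primary endpoint.** Section 7.3 also uses laboratory data, vital signs and ECG changes.
- **Isolated laboratory changes.** Under 6.4.3 these become AEs only if they meet SAE or DLT criteria or lead to discontinuation. Otherwise they are mostly outside AE counts under either rule, and they are still summarised in the study report.
- **Wrong escalation decisions.** DLTs have their own attribution test in 5.1.4. Under 5.1.7 the dose escalation committee reviews all available safety data, of which AEs of Grade 2 or higher are one item.
- **A uniform downward bias.** Cell 3 runs the other way.
- **Lost comparability with the US study MI-CP184.** Its AE rules are not in the protocol. Malignant neoplasm progression, listed among its SAEs in 2.2.2, would normally be excluded under the 6.4.3 standard as well.

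**Conclusion.** The contradiction is real and should be corrected. Two sections that govern the same AE record use tests that differ in kind, disagree in two of four cells, and have no order of precedence. AE and SAE counts, one component of the primary safety and tolerability endpoint, can therefore change with the section that is followed. Under-reporting of possible drug effects is the main risk, because cell 2 holds the foreseeable symptoms of less than certain cause. That cell 2 is commoner than cell 3 is a judgement about this population, not a figure from the protocol.

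One reclassified subject is worth 16.7 to 33.3 percentage points in a cohort of six or three. The number of subjects affected is unknown. The documents do not show any change in DLT counts, in 3+3 decisions or in the MTD.

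**What to change.** Replace the exception in 6.4.1 with the standard that 6.4.3 already uses. Only events unequivocally due to progression of the disease under study, including new or progressing metastases as 6.4.3 provides, are not reported as AEs. All other deterioration, foreseeable or not, is recorded with a causality rating.

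In 6.4.3, change the looser wording in the sub-section on examinations and tests to the same standard. Align the second bullet on deaths too, so that the two bullets cover every death between them.

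The separate limits on when an isolated laboratory change counts as an AE can stay as they are. The change affects recording only and takes one sentence plus two small edits. A few more AEs will be recorded, and the AE tables will be slightly longer.

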### **6.4.2 Definitions of serious adverse events**

A SAE is an AE occurring during any study phase (ie, run-in, treatment, washout, follow-up), that fulfils one or more of the following criteria:

- Results in death
- Is immediately life-threatening
- Requires in-patient hospitalisation or prolongation of existing hospitalisation (including hospitalisation for tests related to AEs), except hospitalisation that has been planned before enrolment

Date

- Results in persistent or significant disability or incapacity
- Is or results in a congenital abnormality or birth defect
- Is an important medical event that may jeopardise the subject or may require medical intervention to prevent one of the outcomes listed above.

For further guidance on the definition of a SAE, see Appendix B of this Clinical Study Protocol.

For definition of other significant adverse events (OAE) see Section 7.3.1.

### **6.4.3 Recording of adverse events**

#### **Time period for collection of AEs**

All AEs will be collected throughout the study, from informed consent until the end of the follow-up period. The follow-up period is defined as 30 days after the end of study treatment.

#### **Follow-up of unresolved AEs**

Any AEs that are unresolved at 30 days after the last study treatment are followed up and written in the medical record by the investigators for as long as medically indicated, but without further recording in the CRF. AstraZeneca retains the right to request additional information for any subject with ongoing AE(s) at the end of the study, if judged necessary.

If an investigator learns of any SAEs, including death, at any time after a subject has completed the study and he/she considers there is a reasonable possibility that the event is related to MEDI-573, the investigator should notify AstraZeneca.

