#### **Subject Evaluation/Follow-up**

A schedule of screening, treatment visit and follow-up visit procedures are presented in [Table 5](#) (Cohorts 1 and 2) and [Table 9](#) (Cohort 3).

The details of the evaluations are shown in Section 6.1.

[figure not shown]
AEs and SAEs during the study will be assessed from the time the subject provides the consent through 30 days after the last dose of MEDI-573. AEs will be graded according to the National Cancer Institute Common Terminology Criteria for Adverse Events Version 4.0 (NCI CTCAE V4.0). In addition, disease evaluations (including computerised tomography (CT) or magnetic resonance imaging (MRI) scans), focused physical examination, and world health organization (WHO) performance status will be performed after every 2 cycles of treatment until documentation of disease progression or initiation of alternative anticancer therapy. For subjects who discontinue treatment due to reasons other than disease progression or initiation

Date

of alternative anticancer therapy, disease evaluations will be performed at 3 months after the last dose of MEDI-573. Subjects will be evaluated for disease response using Response Evaluation Criteria in Solid Tumours (RECIST ver 1.1; [Eisenhauera et al 2009](#)).

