### **5.5 Study timetable and end of study**

Planned duration of the study:

Study period:

Registration period:

There will be an interim data cut-off defined as the earlier of 6 months after the last subject recruited starts investigational product or 3 months after the final subject discontinues investigational product. Data analysis will be performed and a Clinical Study Report written based on this data set.

Any subjects still receiving investigational product at the time of this data cut-off will be able to continue to receive MEDI-573 while deriving clinical benefit. Such subjects will continue to be monitored and all safety assessments performed until the investigational product is discontinued. In addition, these subjects should be followed up for 3 months after the last dose for any new reports of AEs. A Clinical Study Report Addendum may be prepared to summarise the additional safety data collected between the interim data cut-off and the end of the study.

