#### **Variables**

The following variables will be collected in the CRF for each AE:

- AE (verbatim)
- The date when the AE started and stopped
- CTCAE grade
- Whether the AE is serious or not
- Investigator causality rating against the MEDI-573 (yes or no)
- Action taken with regard to MEDI-573
- Outcome

For SAEs additional variables will be collected including treatment given for the event.

Date

It is important to distinguish between serious and severe AEs. Severity is a measure of intensity whereas seriousness is defined by the criteria in Section 6.4.2. An AE of severe intensity need not necessarily be considered serious. For example, nausea that persists for several hours may be considered severe nausea, but not a SAE. On the other hand, a stroke that results in only a limited degree of disability may be considered a mild stroke but would be a SAE.

The grading scales found in the revised NCI CTCAE version 4.0 will be utilised for all events with an assigned CTCAE grading. For those events without assigned CTCAE grades, the recommendation in the CTCAE criteria that converts mild, moderate and severe events into CTCAE grades should be used.

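### CRF outcome and stop date are frozen 30 days after the last dose for unresolved AEs, although the site goes on following them and has a 3-month contact: a minor gap in AE outcome data that is cheap to close

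*Protocol*

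**What the plan says.** - **AE window.** Section 6.4.3 states: "The follow-up period is defined as 30 days after the end of study treatment". Section 3.1 sets the same window, "from the time the subject provides the consent through 30 days after the last dose of MEDI-573".
- **CRF content.** The variables recorded for each AE in Section 6.4.3 include "The date when the AE started and stopped" and the outcome.
- **AEs still open at 30 days.** Section 6.4.3 has the investigator follow them in the medical record "for as long as medically indicated, but without further recording in the CRF". The next sentence adds a reserve: "AstraZeneca retains the right to request additional information for any subject with ongoing AE(s) at the end of the study, if judged necessary".
- **SAEs.** Section 6.4.4 requires SAEs to be in the CRF. It also requires follow-up information to go to the sponsor, including outcome and, if available, stop date.
- **3-month contact.** Section 6.3.6: "IM and preliminary anti-tumour activity will be evaluated at the follow-up, which occurs 3 months after the last dose". Tables 5, 9, 13 and 14 schedule the antibody sample then. Tables 5 and 9 schedule no AE assessment, laboratory safety test, vital signs or ECG at that time.
- **Use of the data.** Section 7.3 assesses safety through AEs, laboratory data, vital signs and ECG. It names no endpoint for resolution or duration. Section 7.9 allows no imputation.

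**The concern.** The protocol asks for an outcome and a stop date for each AE, keeps the investigator following the open ones, and brings the subject back at 3 months. Yet it bars the result of that follow-up from the trial database. A DLT, or an AE that ended treatment, that is open at 30 days and gone by 3 months would be listed as unresolved.

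Safety and tolerability is the primary objective, and only 9 to 18 evaluable subjects are planned. Whether the few important toxicities lasted or faded slowly is something a reader of the study report will want to know, and the CRF would not tell them.

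**Working it through.** The protocol gives no figure to reproduce. The check is a reading of the passages side by side, followed by arithmetic for scale.

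**1. What freezes.** Stop date and outcome are CRF fields. CRF entry for open AEs ends at 30 days. An AE that resolves later therefore keeps its 30-day outcome and has no stop date, and nothing is imputed.

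**2. What does not freeze.** DLTs are assessed over Cycle 1, Days 1 to 21 (Section 5.1.4). Escalation and MTD depend on DLT counts (Sections 5.1.3 and 5.1.5). AE incidence, seriousness and causality, and the grades behind DLTs and escalation, do not depend on whether an event resolves after day 30.

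**3. Length of the gap.** Take 3 months as 90 to 92 days (assumption). The visit windows are +3 days at 30 days and ±14 days at 3 months.
- Shortest: (90 − 14) − (30 + 3) = 76 − 33 = 43 days.
- Longest: (92 + 14) − 30 = 106 − 30 = 76 days.

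**4. Which AEs are likely to be open.** From Cycle 2, the rules in Section 5.1.8 tend to select slow-resolving toxicities.
- Cohort 3 (Table 4): one trigger for stopping is a Grade 2 to 4 toxicity not resolved by Day 1 of the next cycle, about 21 days after the last dose. CRF recording then closes about 30 − 21 = 9 days later.
- Cohorts 1 and 2 (Table 3): one trigger is withholding for more than 7 days without resolution. With weekly dosing this comes more than about 7 + 7 = 14 days after the last dose, leaving at most about 30 − 14 = 16 days.

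**5. How many.** The protocol gives no rate of unresolved AEs, so the number affected cannot be computed. For illustration only, suppose the time from last dose to resolution is exponential, S(t) = 0.5^(t/median), with the 3-month visit at day 91. None of these medians comes from the protocol.

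| Assumed median (days) | Open at day 30: S(30) | Resolving between day 30 and day 91: S(30) − S(91) |
|---|---|---|
| 7 | 5% | 0.051 − 0.000 = 5% |
| 14 | 23% | 0.226 − 0.011 = 22% |
| 30 | 50% | 0.500 − 0.122 = 38% |
| 45 | 63% | 0.630 − 0.246 = 38% |
| 60 | 71% | 0.707 − 0.350 = 36% |

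The percentages are of AEs still open at the last dose, a count that is unknown.

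**6. A rough base.** Section 2.2.2 reports 25 subjects in the US study: no DLT, no SAE judged related, and 6 subjects who stopped for an AE, 1 of them for an AE judged possibly related. If those rates carried over to 9 to 18 subjects (assumption):
- possibly related stops: 9 × 1/25 = 0.4 to 18 × 1/25 = 0.7;
- all AE-related stops: 9 × 6/25 = 2.2 to 18 × 6/25 = 4.3.

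Only some of these would be open at day 30.

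**The case against.** The 30-day limit is deliberate and is stated consistently in Sections 3.1, 6.4.1 and 6.4.3. It is a boundary on data capture, not an error. The later information stays in the medical record and the sponsor may ask for it. Late SAE outcomes reach the sponsor under Section 6.4.4. No endpoint for resolution or duration is named, and few important events are to be expected. All of this stands, and it is why the point is minor.

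Three parts of the objection carry less weight. The right to request information is discretionary and names neither a criterion nor a data field. The SAE route does not cover non-serious DLTs, Grade 3 AEs or AEs that end treatment. It also means that an SAE can be resolved in the SAE reports and unresolved in the CRF.

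A reader might infer more than the documents support:
- **That the primary safety results are distorted, or that the information is lost.** Only outcome and duration in the CRF are affected, and the source record survives.
- **That Section 5.5 contradicts this rule.** It says of subjects still on drug at the data cut-off that "these subjects should be followed up for 3 months after the last dose for any new reports of AEs". That concerns new AEs, not the outcome of recorded ones. Its mismatch with the 30-day window is a separate matter to reconcile.
- **That half or more of open AEs would be affected.** That holds only if the assumed median is 30 days or longer.
- **That the 3-month contact is a safety visit.** It is not. Regrading laboratory-based AEs there would need added tests. Concomitant medication recording also ends at 30 days (Section 4.3.1), so a late resolution could not be read against later treatment.

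**Conclusion.** The concern holds in a narrow form. For AEs that resolve more than 30 days after the last dose, the CRF will show the 30-day outcome and no stop date, although the investigator is still following them and sees the subject at 3 months. This weakens only the description of AE outcome and duration, chiefly for non-serious DLTs, related Grade 3 or higher AEs and AEs that end treatment. For SAEs the effect is a possible disagreement between the CRF and the SAE reports.

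The size cannot be derived from the protocol. The table above is only a range under assumed medians, and the US experience suggests a handful of subjects at most. The conclusion assumes that the 3-month antibody sampling takes place as scheduled. It is a minor point, worth acting on because the change is small.

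**What to change.** Amend the clause in Section 6.4.3. The updated AEs would be those ongoing at 30 days that are serious, are DLTs, are Grade 3 or higher and related to MEDI-573, or caused discontinuation. For these, update the last known outcome and stop date in the CRF up to the 3-month visit, from information the site already holds or obtains at that contact. Require no new tests. State in the report the date as of which outcome is given. Align Sections 6.4.3 and 6.4.4 so that the CRF and the SAE reports give the same outcome for an SAE.

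Updates that arrive after the data cut-off can go into the addendum foreseen in Section 7.10.2.

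Cost: a protocol wording change, one AE status question at the 3-month contact, and a few more data queries.
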